**Strategy to address multiplicity**

Hypothesis testing for analyses of the primary outcome will follow the closed testing procedure, whereby there is initially a test of the null hypothesis that the incidence in the three groups is the same. If this is rejected at the 5% level, pairwise comparisons will be done also using a 5% significance level. Pairwise comparisons can be considered statistically significant only if the overall null hypothesis is rejected. P-values and 95% confidence intervals will be presented.

For the non-inferiority comparison of the primary outcome described above, we will calculate two-sided 95% confidence intervals, equivalent to the use of a one-sided significance level of 2.5%, as is recommended (4). To illustrate the level of confidence with which non-inferiority can be declared, we will plot the point estimate for the hazard ratio with two-sided 90, 95 and 99% confidence intervals, and the non-inferiority margin (a hazard ratio of 1.2, which would reflect 20% higher incidence of clinical malaria in children in the RTS,S/AS01E alone group, relative to the SMC alone group).

For secondary outcomes, we will present 95% confidence intervals, without adjustment for multiplicity, stating that no adjustment was made.

For safety outcomes, we will present p-values and 95% confidence intervals, without adjustment for multiplicity.

### **Trial profile – Original Study**

The original trial profile showed the number of individual children enumerated at the initial census, the number of children eligible, and the number of children for whom consent was obtained. The profile also showed, for all the eligible children seen at the census who were randomised, the number of children seen at the first study contact who received the first dose of vaccine and who joined the study.

The number of children who exited the study population by the end of the first, second and third year of the original trial were shown, with reasons (where known) tabulated.

Uptake of the study interventions will be summarised, including:

- the number that received different combinations of vaccine doses;
- the distribution of the interval between doses;
- the number that received 0,1,2,3,4 SMC treatments each year;
- the actual timing of SMC cycle 1 in relation to the malaria transmission season;
- the mean and range of the intervals between the monthly SMC courses;
- the adherence to daily doses of SMC each month

Separate profiles were produced for each of the two trial centres.

### **Trial Profile - Extension Study**

The number of individuals eligible to join the two-year extension study, and the number who gave consent to participate will be shown.

The number of children who exited the study population by the end of the fourth (2020 intervention year) will be tabulated with reasons (where known) indicated.

Children who reached the age of 5 years prior to the 2021 intervention year will be shown as a separate category (this does not count as 'loss to follow-up' as these children were excluded from further intervention by design, and continued to be monitored for longer-term for morbidity post-intervention).

Among children who remained below the age of five years in June 2021, the number of children who exited the study population by the end of the fifth (2021 intervention year) will be tabulated, with reasons (where known) indicated.

Uptake of the study interventions during the intervention period will be summarised, including:

- the number that received different combinations of vaccine doses;
- the distribution of the interval between doses;
- the number that received 0,1,2,3,4 (and 5 in Burkina Faso, in 2021) SMC treatments each year;
- the actual timing of SMC cycle 1 in relation to the malaria transmission season;
- the mean and range of the intervals between the monthly SMC courses;
- the adherence to daily doses of SMC each month

## Statistical methods

### Reference group

As SMC is the current standard of care, the SMC alone group will be considered as the reference group for comparisons with RTS,S/AS01E alone, and the combined group. Comparisons will also be made between the RTS,S/AS01E alone and the combined group.

### Primary endpoint

#### Hazard Ratios

The hazard ratio for the primary outcome will be estimated using Cox regression models, with a robust standard error (i.e. the Andersen-Gill extension of the Cox model) to account for potential clustering of episodes within children. The Efron method will be used for tied event times.

The timescale will be calendar time. For analyses of the whole study period, calendar time will start from 1st April 2017, i.e. allowing delayed entry according to the precise timing of the first vaccination contact. This ensures that risk sets in the Cox models are comparable with respect to the timing of onset of transmission each year, and the timing of SMC. Due to variable timing in vaccine dose 1 in 2017, this would not be the case if the data were analysed on the time in study timescale. For the same reasons, analyses of the effectiveness of the sixth and seventh doses of RTS,S, calendar time will start from 1st April 2020 and 1st April 2021, respectively (i.e. the beginning of the study year in which the sixth and seventh doses were administered).

Nelson-Aalen Cumulative hazards will be plotted for each group to show the mean number of events per child during the study and the timing of events, and Kaplan Meier failure estimates will be plotted to show the risks during the study.

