#### Extension Study

The extension study, undertaken in children aged three or four years old who had previously received five doses of the RTS,S/AS01E malaria vaccine or comparator vaccines, together with seasonal malaria chemoprevention (SMC) with sulphadoxine-pyrimethamine (SP) plus amodiaquine (AQ) or placebo set out to determine whether :

1. Vaccination with a booster dose of the RTS,S/AS01E malaria vaccine at the beginning of the malaria transmission until children reach the age of five years is non-inferior to SMC in preventing clinical attacks of malaria and would be easier to deliver than SMC.

2. Administration of further doses of RTS,S/AS01 E at the beginning of the malaria transmission until children reach the age of five years provides additional protection against clinical episodes of malaria when given together with SMC.

A key question for policy makers and malaria control programme managers is the impact of the two interventions and their combination in the first five years of life (the age range for which seasonal malaria chemoprevention is the current standard of care in most countries where it is policy). The primary focus of the overall study is, therefore, determination of the impact of the two interventions and their combination over the whole five-year period (the three-year initial study, plus the two-year extension), and its interpretation will, therefore, be based on the cumulative incidence of malaria until children reach the age of five years, and are no longer eligible for SMC.

The primary objective of the extension study is determination of potential added value of extending administration of the two interventions and their combination beyond the age of three years. This will be based on the results obtained in the final two years of the study, based on the objectives described above.

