#### **A) Whole intervention period (all children).**

The primary analysis population will be the whole intervention period. This is the period starting from enrolment in April 2017 until the end of the intervention year in which children reached 5 years of age (31 March 2021 for *older children*, 31 March 2022 for *younger children*).

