## Analysis strategy

### Modified Intention to Treat

The primary analysis will be by modified intention to treat (mITT). The mITT population will include all children who were screened and who received the first dose of RTS,S/AS01E or control vaccine, irrespective of the number of doses of subsequent vaccines or SMC/SMC placebo received.

Children will contribute time at risk from the date of the first vaccination contact in 2017, until the end of the intervention period, which is either

- i) 31st March 2021, if born prior to 1st June 2016 (and thus over the age of five years in June 2021), or
- ii) 31st March, 2022, if born on or after 1st June 2016, and thus still under the age of five year in June 2021.

Prior to the end of the intervention period, children may be censored;

- 1) on the date last seen if lost-to-follow-up (LT FU),
- 2) on the date of permanent exit from the study area, or
- 3) on the date of death,

Children who temporarily left the study area with known exit and re-entry dates will have the corresponding person-time excluded from the analysis by intention to treat (and per protocol, if leaving the study area does not result in missed treatments).

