### Incidence rate differences

In addition to the hazard ratios from Cox regression, as described above, the incidence rate differences (IRD) will also be calculated, i.e. the cases averted per 1000 child-years at risk. This is recommended in the updated CONSORT guidelines (8), as this gives an indication of the reduction in incidence attributable to the interventions, i.e. the absolute public health impact in similar contexts. This is an important question for the overall effect of the two interventions under study in this trial, which is a question of key interest for policy makers. This is also relevant to the interpretation of efficacy over successive years of the study. For example, if the hazard ratio between the intervention groups moves towards unity as children become older, but malaria incidence increases in older children, the absolute impact of the interventions could remain as important (or even more important), in older children. Alternatively, if the hazard ratio remains similar to that seen in the initial intervention period but incidence falls in older children, extension of vaccination into older children may not be warranted.

The IRD will be calculated using ordinary least squares regression of transformed variables for the intervention group, country and person-time at risk, as described by Xu et al. (9). This method uses a robust standard error and controls for unequal follow-up time, as well as

quantitative or multiple covariates. To aid interpretation, the risk of the primary outcome will also be estimated from the Kaplan-Meier estimate of the risk.

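### The pooled Period A Nelson-Aalen and Kaplan-Meier curves treat older children's planned stop in March 2021 as ordinary censoring, so their March 2022 values exceed mean episodes and risk per child to the age-five stop

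*Combined protocol and SAP*

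**What the plan says.** The SAP section on hazard ratios states that "Nelson-Aalen Cumulative hazards will be plotted for each group to show the mean number of events per child during the study" and that "Kaplan Meier failure estimates will be plotted to show the risks during the study". The same section says "The timescale will be calendar time". The section on incidence rate differences adds that "the risk of the primary outcome will also be estimated from the Kaplan-Meier estimate of the risk". Dummy Figure 1 makes both curves a planned main figure.

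The primary analysis population is Period A, which has two planned end dates: "31 March 2021 for *older children*, 31 March 2022 for *younger children". Under modified intention to treat, the SAP says "Prior to the end of the intervention period, children may be censored" and then lists loss to follow-up, permanent exit and death. Reaching the age limit is not on that list, and the extension-study trial profile says that it is not loss to follow-up.

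Under study objectives, the SAP says that interpretation of the overall study will be "based on the cumulative incidence of malaria until children reach the age of five years, and are no longer eligible for SMC". It does not say how the curves handle the planned stop, or what a pooled curve means after 31 March 2021.

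**The concern.** Older children do not go missing in March 2021. Their intervention period is complete, and the quantity that the SAP will interpret ends for them on that date. A Nelson-Aalen or Kaplan-Meier estimate on calendar time removes them from the risk set and carries the whole cohort forward at the younger children's fifth-year hazard. The value at March 2022 then combines years 1 to 4 from all children with year 5 from a minority or, at most, half of them.

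That value is not the mean per child over Period A. It is not Period D, which ends in March 2021, nor Period E, which uses younger children throughout. A reader who takes the end of the main figure as episodes per child, or risk, up to the age-five stop would read both too high in every arm.

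**Working it through.** **Inputs**
- Incidence in SMC alone, years 1 to 3: 305 per 1000 child-years (SAP, superiority comparison).
- Planning incidence: at least 200 per 1000 over the whole study (same section), and about 200 in the year after the third booster (SAP, analyses in individual years). Using 200 for year 5 as well is an extension of this.
- Share of older children, p: 3860/5920 = 65.2% (SAP, analyses in individual years; protocol 10.2), although the wording there is only a little over half; about 60% in protocol 7.6.9. I use 50% (assumption), 60% and 65.2%.
- Combined arm: incidence about 60% lower in years 1 to 3 (SAP, superiority comparison), carried forward as an assumption.

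**The plan's own figure.** The SAP gives no five-year mean or risk. The nearest figure on the same inputs is 90% power for a 12.0% difference. With rates 0.200 and 0.176 and 6875 person-years per group (protocol 10.2): 0.024 / √(0.376/6875) − 1.96 = 1.285, which gives 90.1%. It reproduces.

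**Formulas.** Let H(4) and H(5) be the sums of the yearly rates h1 to h4 and h1 to h5, with every year counted as full.
- Pooled Nelson-Aalen value at March 2022: H(5).
- Mean per enrolled child to the planned stop: p × H(4) + (1 − p) × H(5) = H(5) − p × h5.
- Kaplan-Meier value: 1 − exp(−H(5)), compared with p × [1 − exp(−H(4))] + (1 − p) × [1 − exp(−H(5))].

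**SMC alone**

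| Yearly rates | p | Nelson-Aalen | Mean to stop | Excess | KM risk | Risk to stop | Excess |
|---|---|---|---|---|---|---|---|
| 0.200 in all years | 50% | 1.000 | 0.900 | 11.1% | 63.2% | 59.1% | 6.9% |
| | 60% | 1.000 | 0.880 | 13.6% | 63.2% | 58.3% | 8.4% |
| | 65.2% | 1.000 | 0.870 | 15.0% | 63.2% | 57.9% | 9.2% |
| 0.305 in years 1–3, then 0.200 | 50% | 1.315 | 1.215 | 8.2% | 73.2% | 70.2% | 4.2% |
| | 60% | 1.315 | 1.195 | 10.0% | 73.2% | 69.6% | 5.1% |
| | 65.2% | 1.315 | 1.185 | 11.0% | 73.2% | 69.3% | 5.6% |

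Allowing children to differ in underlying risk (gamma frailty, shape 1) lowers the Kaplan-Meier excess slightly, for example from 9.2% to 7.8%.

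**Sensitivity to year 5 (assumed rates, p from 50% to 65.2%).**
- 305 in years 1–3, 200 in year 4 and 100 in year 5: the Nelson-Aalen excess is 4% to 6%.
- 200 in years 1–4 and 400 in year 5: 20% to 28%.
- 200 read as the exact five-year average after 305 in years 1–3, so that years 4 and 5 are (1.000 − 0.915)/2 = 0.0425 each: 2% to 3%.

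**Combined arm, p = 65.2%.** Kaplan-Meier risk is 33.0% against 29.3% at the flat rate (12.4% too high), and 40.9% against 37.7% with 305 then 200 as the SMC rates (8.5% too high).

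**Gap between SMC alone and Combined, p = 65.2%.** Subtracting the Nelson-Aalen curves gives 0.600 against 0.522 per child (15% too large), or 0.789 against 0.711 (11%). A Kaplan-Meier risk difference is 2% to 6% too large.

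**Simulation.** At a flat 200 with 5% annual loss to follow-up, the Nelson-Aalen end value was 1.001. Mean episodes per enrolled child over planned follow-up, without loss, were 0.870. The rate was 200.1 per 1000 child-years.

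**The case against.** The strongest reply is that the curve has another valid target. A right-censored cumulative hazard at five years estimates expected episodes over five intervention years, and the SAP also describes its focus as the whole five-year period. That reading is coherent, but it requires the younger children's fifth-year rate to apply to the older children, and the SAP itself plans to examine effect modification by age at enrolment. The SAP already defines the full five-year course as Period E, in younger children only, and it states its basis for interpretation as incidence to the point where SMC eligibility ends.

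A second reply is that the information appears elsewhere. Period D will be split by age in June 2021, Period E is separate, Dummy Table 1 gives events and children per arm, and the example figure carries a number-at-risk row. These would let a careful reader notice the change in risk set. They do not change the value at the end of the curve.

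Other objections stand. The size depends on an unknown fifth-year incidence, which the SAP expects may decline. The weighted average proposed below is not incidence from birth either: older children were already about 11 to 17 months old at entry, so it describes enrolled children over planned follow-up.

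A reader might also infer that the trial's cases averted are overstated by a tenth. The documents do not support that. Cases averted are planned as an incidence rate difference per 1000 child-years, from a person-time regression that allows for differing follow-up; at a flat 200 and a 60% reduction it is 120 per 1000 whichever way the curves are drawn. Only a gap read off the Nelson-Aalen curves would be inflated by that much. Nor does the Nelson-Aalen percentage carry over to risk, where the excess is smaller.

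**Conclusion.** The point holds for two descriptive outputs: the end of the pooled Period A curves, and any Kaplan-Meier risk reported from them. It applies if the curves are drawn for Period A as the SAP now reads. Mean episodes per child would be about 8% to 15% too high on the documents' rates with an older share of 50% to 65%. Kaplan-Meier risk would be about 4% to 9% too high in SMC alone, and about 9% to 12% in Combined at 65% older. The excess shrinks if fifth-year incidence falls and grows if it rises.

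The hazard ratios, the comparison with the 1.2 margin, the closed tests, the incidence rate difference and the single-year malaria-free proportions are not affected. The change is still worth making, because the curves are a planned main figure and cumulative incidence to the age-five stop is the stated basis for interpretation.

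**What to change.** In the SAP sections on hazard ratios and incidence rate differences, and in Dummy Figure 1, use the SAP's own older and younger groups. Either draw the curves separately, ending on 31 March 2021 for older children and 31 March 2022 for younger children, or stop the pooled curve at 31 March 2021 and show Period E as its own panel.

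Report Period A mean episodes per child and risk as the average of the two groups' end values. Weight by the share of older and younger children enrolled in each country, with the same weights in all arms, and give a 95% confidence interval by bootstrap over children or by the delta method. Randomisation lists were sorted by age in months within country, so the shares should be close across arms.

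Settle the older share from the enrolment data, since the documents describe it in three ways: a little over half, about 60%, and 3860/5920.

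The cost is a busier figure, some SAP wording and a little extra code. No new data are needed.

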### Incidence rate differences

In addition to the hazard ratios from Cox regression, as described above, the incidence rate differences (IRD) will also be calculated, i.e. the cases averted per 1000 child-years at risk. This is recommended in the updated CONSORT guidelines (8), as this gives an indication of the reduction in incidence attributable to the interventions, i.e. the absolute public health impact in similar contexts. This is an important question for the overall effect of the two interventions under study in this trial, which is a question of key interest for policy makers. This is also relevant to the interpretation of efficacy over successive years of the study. For example, if the hazard ratio between the intervention groups moves towards unity as children become older, but malaria incidence increases in older children, the absolute impact of the interventions could remain as important (or even more important), in older children. Alternatively, if the hazard ratio remains similar to that seen in the initial intervention period but incidence falls in older children, extension of vaccination into older children may not be warranted.

The IRD will be calculated using ordinary least squares regression of transformed variables for the intervention group, country and person-time at risk, as described by Xu et al. (9). This method uses a robust standard error and controls for unequal follow-up time, as well as

quantitative or multiple covariates. To aid interpretation, the risk of the primary outcome will also be estimated from the Kaplan-Meier estimate of the risk.

### **Proportion of children remaining free of malaria in individual years of the study**

The proportion of children who remained free of malaria (1-risk), in individual study years will be calculated from the Kaplan-Meier estimates in each intervention group. The difference in this proportion between arms, with a 95% CI, and the relative difference (% increase in fraction remaining free of malaria) will also be calculated and presented.

### **Secondary endpoints**

Secondary outcomes which are passively detected events, will be analysed in a similar way as for the primary outcome, i.e. estimating the hazard ratio using Cox regression with a robust standard error.

The prevalence ratio of secondary endpoints measured at the weekly survey (aggregated into three-month periods), and at end of season surveys (including *P. falciparum* parasitaemia, anaemia, etc) will be estimated using Poisson regression, with a robust standard error for the individual, as described in Zou, 2004 (10).

Linear regression models will be used to compare mean haemoglobin concentration between the groups.

Arithmetic mean parasite densities (including in the calculation samples which are parasite negatives, as having density of zero), will be compared between arms using Poisson regression with a robust standard error.

### **Covariates**

All analyses (primary outcomes and secondary outcomes) will stratify on study country only (Burkina Faso or Mali).

For the primary outcome, we will also build a model adjusting for the following potential confounders:

- Age at enrolment
- Child's Sex
- Bednet use at baseline in 2017

### **Pre-specified subgroup analyses, interactions and exploratory analyses**

As described above, the primary analysis will be pooled across the two study centres, stratified by (i.e. adjusted for) country. Efficacy (ratio and difference) measures will be presented for both sites combined. Investigation of any differences in intervention effects between the centres (formally, evidence for an interaction between intervention group and study centre) is pre-specified due to possible differences in performance of these interventions under different malaria transmission intensity. All outcomes will, therefore, also be tabulated by centre, and site-specific efficacy estimates will be presented.

Investigation of differences between study groups in each study year is also pre-specified, as described above, because it is possible that the efficacy of RTS,S/AS01 booster doses changes over time, or following successive doses. This will be assessed by exploring evidence for an interaction between intervention group and study year.

Evidence for effect modification by age at enrolment will be explored. It is possible that vaccination will perform differently according to the extent of prior exposure to malaria. As described above, analyses of the first four years of the study (analysis population D) will be conducted splitting children according to their age in June 2021 (children aged 5 years or more, vs. children who were still under 5 years; younger children subsequently received an extra year of intervention).

Finally, evidence for effect modification by child's sex (observed in the RTS,S Phase III trial) will be explored by inclusion of an interaction term in the Cox models for the primary outcome over the whole analysis period (period A). Severe malaria meeting the WHO definition and malaria deaths will also be included as exploratory analyses.

